**7.12.6.8 The mean change in PainDETECT from Baseline (D1) to Week 4 and Week 12.**

PainDETECT is a 7-question validated tool to determine the prevalence of neuropathic pain in individuals with lower back pain. The 7 responses, with possible values of never (0), hardly noticed (1), slightly (2), moderately (3), strongly (4), and very strong (5), are summed for a possible score ranging from 0-35. In addition to the 7 questions, subjects note the course of pain (Persistent pain with slight fluctuations; Persistent pain with pain attacks, Pain attacks without pain between them; Pain attacks with pain between them) with 0, -1, 1, and 1 score assignments respectively, and whether the pain radiates to other regions of the body or not which adds 2 to the total score for a “yes” response and 0 for a missing or “no” response. Hence, the total overall scale score will range from 0 to 38. Baseline PainDETECT total score is defined as the last score collected prior to the first injection on D1. Since this endpoint is summing the responses to get the total score, if a subject is missing a question aside from the question on whether the pain radiates to other regions of the body or not, the total score will not be calculated for that subject. PainDETECT will be collected at Baseline (D1), Week 4, and Week 12.

PainDETECT at Week 4 will be analyzed using an ANCOVA model with change from baseline at Week 4 as the response variable with fixed effects for treatment (two groups: SP102 or placebo), site, Pain Catastrophizing Scale group (<30 or ≥30), and baseline PainDETECT total score.

Change from baseline to Week 12 will also be analyzed using an MMRM analysis with change from baseline to Week 12 (Weeks 4 and 12) as the response variable, with fixed effects for treatment (SP-102/SP-102, PBO/SP-102, SP-102/none, PBO/none) week, site, Pain Catastrophizing Scale group ( $<30$  or  $\geq 30$ ), baseline score, and treatment-by-week interaction. As part of this analysis, comparisons will test the mean LS mean differences between the following groups:

- SP-102/none vs. PBO/none
- SP-102/SP-102 vs. PBO/none
- SP-102/none vs. PBO/SP-102
- SP-102/SP-102 vs. PBO/SP-102

Pain*DETECT* will be summarized for Week 24 by treatment (four groups).

#### **7.12.6.9 The mean change in BPI-SF score from Baseline (D1) to Week 4 and Week 12.**

The BPI-SF is a 15-item self-rating scale assessing use of medications, as well as sensory, and reactive components of pain. The BPI-SF includes items that will address components of sensory pain, including severity, location, chronicity, and degree of relief due to therapy. The BPI-SF also has items that address reactive pain components, including depression, suffering, and perceived availability of relief. The BPI-SF will be collected at Screening, Baseline (D1), Week 4 (Day 29), and Week 12 visits. Two BFI-SF scales will be derived from the BRI-SF responses: Pain Severity Score and Pain Interference Score.

Pain Severity Score = Mean of items 3-6 (pain at its worst, pain at its least, average).

Pain Interference Score = Mean of items 9A-9G (interference of pain with: general activity, mood, walking, normal work, relations, sleep, enjoyment of life).

BPI-SF at Week 4 will be analyzed using an ANCOVA model with change from baseline at Week 4 as the response variable with fixed effects for treatment (two groups: SP102 or placebo), site, Pain Catastrophizing Scale group ( $<30$  or  $\geq 30$ ), and baseline score. Baseline BPI-SF scale score is defined as the last BPI-SF assessment scale score prior to first injection on Day 1.

Change from baseline to Week 12 will also be analyzed using an MMRM analysis with change from baseline to Week 12 (Weeks 4 and 12) as the response variables, with fixed effects for

treatment (SP-102/SP-102, PBO/SP-102, SP-102/none, PBO/none), week, site, Pain Catastrophizing Scale group ( $<30$  or  $\geq 30$ ), baseline score, and treatment-by-week interaction. As part of this analysis, post-hoc comparisons will test the mean LS mean differences between the following groups:

- SP-102/none vs. PBO/none
- SP-102/SP-102 vs. PBO/none
- SP-102/none vs. PBO/SP-102
- SP-102/SP-102 vs. PBO/SP-102

BPI-SF scores will be summarized for Week 24 by treatment (four groups).

#### **7.12.6.10 Proportion of subjects achieving a response of 30%, 50%, and 75% reductions from Baseline (D1) in mean NPRS average pain score in the affected leg at Week 2 and Week 4.**

Responders are defined and calculated as follows:

30% responder =  $(\text{Change from baseline} / \text{baseline}) \times 100 \leq -30$ .

50% responder =  $(\text{Change from baseline} / \text{baseline}) \times 100 \leq -50$ .

75% responder =  $(\text{Change from baseline} / \text{baseline}) \times 100 \leq -75$ .

Subjects that discontinue or have missing scores at Week 2 and Week 4 will be considered non-responders.

The proportion of subjects achieving a response will be analyzed for each cut off percentage (30%, 50%, and 75%) by week. This will be analyzed using a Chi-Square test where the p-value of the treatment difference will be presented. For each cutoff response percentage, a logistic regression models with treatment (two groups: SP102 or placebo), site, Pain Catastrophizing Scale group ( $<30$  or  $\geq 30$ ), and baseline averaged daily leg pain score as factors will also be used to compare the treatment groups at each week. The odds ratio of SP-102 vs placebo, its corresponding 95% CI and p-value will be presented. The number and percentage of responders will be presented for each visit.

A continuous responder analysis will also be performed. The proportion of subjects achieving a reduction in pain will be plotted against the continuous cutoff ranging from 0% to 100% reduction in pain intensity from Baseline (D1) as measured by the NPRS average daily leg pain scores in the

affected leg. This analysis will be performed using data observed at Week 4 and then over the first 4 weeks (using average of the 4 weekly mean NPRS average daily leg pain scores in the affected leg to calculate the percent reduction). All subjects who withdraw early from the study within 4 weeks will be considered non-responders. Treatment groups (SP-102 and placebo) will be compared using a log rank test.

**7.12.6.11 The mean change from Baseline (D1) to Week 2, Week 4, Week 8, and Week 12 in mean NPRS average pain score in the lower back.**

The average pain score in the lower back is measured at every clinic visit. This endpoint will be analyzed and presented using the same MMRM model described in the primary analysis but the response variable will be change from baseline in mean NPRS average pain score in the lower back at Weeks 2, 4, 8, and 12; with baseline NPRS score as the last score collected prior to the first injection on D1. Mean change from baseline for the first 4 weeks (Week 2 and Week 4) will be analyzed and presented by the treatment received for the first injection (SP-102, Placebo). Mean change from baseline for the first 12 weeks (Weeks 2, 4, 8, and 12) will also be analyzed and summarized by treatment received for second injection (SP-102/SP-102, PBO/SP-102, SP-102/none, PBO/none). As part of this analysis, comparisons will test the mean LS mean differences between the following groups:

- SP-102/none vs. PBO/none
- SP-102/SP-102 vs. PBO/none
- SP-102/none vs. PBO/SP-102
- SP-102/SP-102 vs. PBO/SP-102

NPRS average scores are also collected at visits (Weeks 16, 20, and 24) after visit 12. This data will not be included in the model but will be included in the summary table.

**7.12.6.12 CGIC at Week 2, Week 4, Week 8, and Week 12.**

The CGIC is an 8-point scale (0 to 7, where 0 is not assessed, 1 is very much improved, and 7 is very much worse) that allows clinicians to rate the subject's global impression of change. CGIC will be collected after randomization at Weeks 2, 4, 8, 12, 16, 20, and 24. For analysis, a subject will be classified as either CGIC responder, that is, a CGIC response of 1: very much improved or 2: much improved or a CGIC non-responder, that is, all other CGIC responses (recorded as 3-7 in the scale). Subjects who do not complete the measure at the timepoint of interest will also be considered non-responders. The number and percentage of subjects reporting each of the seven

CGIC response levels will also be summarized by visit and treatment. Analyses will utilize separate Chi-Square tests for Week 2 and Week 4 where the p-value of the treatment difference will be presented. Separate logistic regression models with treatment, site, and Pain Catastrophizing Scale group ( $<30$  or  $\geq 30$ ) as factors will also be used to compare the treatment groups for Week 2 and Week 4 using the 2 treatment groups. The odds ratio of SP-102 vs placebo at Weeks 2 and 4, and its corresponding 95% CI and p-value will be presented. Listings of CGIC will also be provided.

Separate Chi-Square tests and similar logistic regression analyses will be applied at Weeks 2, 4, 8, and 12 using the treatment group with four arms: SP-102/SP-102, PBO/SP-102, SP-102/none, PBO/none. The following odds ratios at Weeks 2, 4, 8, and 12 and the corresponding 95% CIs and p-values will be presented:

- SP-102/none vs. PBO/none
- SP-102/SP-102 vs. PBO/none
- SP-102/none vs. PBO/SP-102
- SP-102/SP-102 vs. PBO/SP-102

A summary of the assessments at Weeks 16, 20, and 24 will be presented.

#### **7.12.6.13 Cumulative use of rescue medication (mg of acetaminophen)**

In this study, acetaminophen is the permitted and study-provided rescue medication. For subjects that withdraw early, their missing weekly values after withdrawal will be imputed using the average weekly score for the respective treatment group. If the subject has partial records of rescue medication on the week of subject's withdrawal, the rescue medication use on that week will be imputed as follows:

[ partial record of rescue medication on the withdrawal week \* (7/number of days in the withdrawal week with partial record) ].

Cumulative use of rescue medication at Week 4 will be obtained as the rescue medication use during the first four weeks relative to the index injection, that is, up to the subject's Day 29 in the study. It will be analyzed using an analysis of variance (ANOVA) model with cumulative use from baseline to Week 4 as the response variable with fixed effects for treatment (two groups: SP102 or placebo), site, and Pain Catastrophizing Scale group ( $<30$  or  $\geq 30$ ). The same ANOVA model will

be applied on only subjects that complete 4 Weeks and output will be presented using the two treatment groups.

Cumulative use of rescue medication at Week 12 will be obtained as the rescue medication use during the first 12 weeks relative to the index injection, that is, up to subject's Day 85 in the study. It will also be analyzed using an ANOVA model with cumulative use from baseline to Week 12 as the response variable with fixed effects using the four treatment (SP-102/SP-102, PBO/SP-102, SP-102/none, PBO/none) variable, site, and Pain Catastrophizing Scale group (<30 or ≥30). The same ANOVA model will be applied on only subjects that complete 12 Weeks and output will be presented using the four treatment groups.

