3.5.5 Assessments for Early Termination

If the subject's participation in the study is terminated prematurely for any reason, the reason for such ET should be documented and the W24 (D169) procedures should be performed. If the ET occurs prior to W4 (D29), the subject should be encouraged to continue in the study until W4 (D29), if possible. In case of ET, the subject should be encouraged to return to the site for ET procedures, or failing a return visit, a telephonic visit should be arranged to encourage the subject to complete the W24 (D169) procedures (Section 3.5.2.11).

An EOS eCRF page should be completed for every subject who receives IP, whether the subject completes the study or not. The reason for any ET should be indicated on this form. The primary reason for the ET should be selected as noted in Section 3.3.3.

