5.2.8.3 Secondary Efficacy Endpoints

The key secondary efficacy endpoint is:

- The change in ODI total score from Baseline (D1) to W4.

Other secondary endpoints are:

- The time to repeat injection of SP-102 from index injection.
- Proportion of subjects receiving repeat injection.
- The mean change from Baseline (D1) to W2, W8, and W12, in the mean NPRS average pain score in the affected leg.
- The mean change from Baseline (D1) to W2, W4, W8, and W12, in the mean NPRS worst pain in the affected leg.

- The mean change from Baseline (D1) to W2, W4, W8, and W12 in the mean NPRS current pain score in the affected leg.
- The mean change from Baseline (D1) in the ODI total score to W12.
- The mean change in PainDETECT from Baseline (D1) to W4 and W12.
- The mean change in BPI-SF score from Baseline (D1) to W4 and W12.
- Proportion of subjects achieving a response of 30%, 50%, and 75% reductions from Baseline (D1) in mean NPRS average pain score in the affected leg at W2 and W4.
- The mean change from Baseline (D1) to W2, W4, W8, and W12 in the mean NPRS average pain score in the lower back.
- PGIC at W2, W4, W8, and W12.
- CGIC at W2, W4, W8, and W12.
- Cumulative use of rescue medication (mg of acetaminophen).
- Time to first rescue medication dose.
- Proportion of subjects requiring rescue medications during first 4 weeks.

Other possible exploratory analyses may be added, such as percent of rescue medication free days, or evaluating certain endpoints only including those data collected prior to a second treatment injection (of SP-102). Any such exploratory additions will be provided in the SAP prior to unblinding.

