## 7.12 Efficacy Analyses

All statistical tests will be performed using a two-tailed 5% overall significance level, unless otherwise stated. All comparisons between treatments will be reported with 95% confidence intervals (CI) for the difference. Pain profiles through the first four weeks will be presented by the treatment received for the first injection (SP-102, Placebo). Moreover, pain profiles through 12 weeks will be presented by treatment received for second injection (SP-102/SP-102, PBO/SP-102, SP-102/none, PBO/none). Also, the ‘site’ indicated in this section refers to the final pooled sites as described in [Section 7.2.10](#).

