**7.12.6.19 Multiplicity**

To control for multiplicity, a sequential testing procedure will be used on the key secondary and other secondary endpoints. Thus, if the primary endpoint is statistically significant, then the key secondary endpoint can be tested. Then if the key secondary endpoint is statistically significant, then the next secondary endpoint can be tested. This will continue until all endpoints have been tested, or until non-significance is observed for an endpoint. The ordering of the tests will follow the order the endpoints listed below:

[Redacted text block containing multiple paragraphs of obscured content]

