## **11 CHANGES TO PLANNED PROTOCOL ANALYSIS**

The following are changes to the planned protocol analysis:

-

- A Screened Population, which consists of subjects that signed the informed consent form and were assigned a user subject number, was added.
- A 12-week Completer, defined as one who receives an injection of study drug and completes the study through Week 12, is added as another type of completer in this trial.
- The following endpoints were updated:
  1. “Week 4” was added to the endpoint “The mean change from Baseline (Day 1) to Week 2, Week 8, and Week 12 NPRS mean average pain score in the affected leg”. The updated endpoint is “The mean change from Baseline (Day 1) to Week 2, Week 4, Week 8, and Week 12 NPRS mean average pain score in the affected leg”.
  2. “during the first 4 weeks” was removed from the endpoint “Proportion of subjects requiring rescue medications during the first 4 weeks”. The updated endpoint is “Proportion of subjects requiring rescue medications”.
- Percent of rescue medication free days, mean change from Baseline (D1) to Week 4 in the mean morning (AM) NPRS average pain score in the affected leg, and mean change from Baseline (D1) to Week 4 in the mean evening (PM) NPRS average pain score in the affected leg were added as endpoints.
- Ordering of the endpoints to be tested for controlling for multiplicity has changed. PGIC which was 13th in the order of endpoints in the protocol was moved to third in order. That is, PGIC will be tested next if the key secondary endpoint is statistically significant.
- [REDACTED]
- An overall summary of the incidence and the number of TEAEs, related TEAEs, SAEs, related SAEs, TEAEs leading to withdrawal, and TEAEs leading to death through 12 weeks and a summary of incidence and number of events of TEAEs by system organ class and preferred term will also be summarized as follows:
  - by four groups (SP-102/SP-102, PBO/SP-102, SP-102/none, and PBO/none)
  - by treatment (Placebo, SP-102) but only for the subjects in the PBO/SP-102 group
  - by exposure to SP-102, that is, Exposed vs. Not Exposed to SP-102; the Exposed group will include the subjects that have received SP-102 for the index injection

and/or have a repeat injection while Non-Exposed group will include the subjects that have received Placebo for the index injection and do not have repeat injection

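### Cumulative rescue use at Week 4: filling weeks after withdrawal with the arm mean and then running an ordinary ANOVA understates the standard error

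*SAP*

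**What the plan says.** SAP 7.12.6.13 handles early withdrawal in two steps. Whole weeks after the subject leaves get a single value: "their missing weekly values after withdrawal will be imputed using the average weekly score for the respective treatment group". The week in which the subject leaves is scaled up from the subject's own diary: the "partial record of rescue medication on the withdrawal week" is multiplied by 7 and divided by the number of recorded days in that week.

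The completed four-week total is the response in an ANOVA with treatment, site and Pain Catastrophizing Scale group. The section provides no multiple imputation, variance correction or adjusted degrees of freedom. The same model will also "be applied on only subjects that complete 4 Weeks and output will be presented using the two treatment groups".

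Two other rules bear on the result. SAP 7.12 sets two-sided 5% tests and requires that "All comparisons between treatments will be reported with 95% confidence intervals (CI) for the difference". SAP 7.12.6.19 states that "a sequential testing procedure will be used on the key secondary and other secondary endpoints", so this endpoint's p-value counts formally if the sequence reaches it.

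**The concern.** Filling with the arm mean adds values that have no residual spread and treats them as data. The pooled variance falls while the nominal sample size stays at its full value, and both effects shrink the standard error. This needs no assumption about why people leave; it happens under completely random dropout.

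The main stake is the reported estimate. Its interval is too narrow and its p-value too small wherever the test sequence stops, because a confidence interval is required for every comparison.

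The stake for confirmatory error is small. SAP 11 says that "PGIC which was 13th in the order of endpoints in the protocol was moved to third in order". Counting the primary endpoint, ODI at Week 4 and then the list in Protocol 5.2.8.3 does put PGIC 13th, and it puts cumulative rescue use 15th. It stays 15th after the move, and the list in SAP 4.3 gives the same place. This is an inference, because the ordered test list is blacked out.

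**Working it through.** The plan states no actual error rate for this analysis, only the nominal 5%, so there is no figure to reproduce.

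**Inputs.** About 400 randomised 1:1, so 200 per arm, and 332 to complete Week 4 (Protocol synopsis). The gap is 68/400 = 17%. This is a planning gap, not a stated dropout rate, so 10% and 5% are shown as well.

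**Large-sample formula, random dropout.** Let p be the fraction of an arm that stays, A a subject's total over the weeks that leavers also have, and B the total over the filled weeks. The filled arm mean equals the mean of A over everyone plus the mean of B over stayers. With n per arm:

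- true variance = [Var(A) + Var(B)/p + 2Cov(A,B)]/n
- variance reported by ANOVA = [Var(A) + p·Var(B) + 2p·Cov(A,B)]/n
- true alpha = 2·(1 − Φ(1.96 × SE ratio)), where SE ratio = reported SE / true SE

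Example: p = 0.83, between-week correlation 0.7, unit weekly variance, leavers observed in Week 1 only. Var(A) = 1, Var(B) = 3 + 6×0.7 = 7.2, Cov = 3×0.7 = 2.1.

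- Reported: 1 + 0.83×7.2 + 0.83×4.2 = 10.46
- True: 1 + 7.2/0.83 + 4.2 = 13.87
- SE ratio = √(10.46/13.87) = 0.868; alpha = 2·(1 − Φ(1.70)) = 8.9%

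| Weeks leavers have | 17% loss: SE ratio, alpha | 10% loss | 5% loss |
|---|---|---|---|
| none | 0.830, 10.4% | 0.900, 7.8% | 0.950, 6.3% |
| 1 | 0.868, 8.9% | 0.924, 7.0% | 0.962, 5.9% |
| 1–2 | 0.911, 7.4% | 0.949, 6.3% | 0.975, 5.6% |
| 1–3 | 0.956, 6.1% | 0.974, 5.6% | 0.987, 5.3% |

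Correlation hardly matters: at 17% loss with Week 1 only, alpha is 8.8% to 8.9% for correlations from 0 to 0.9. A subject who leaves in Week 4 with a scaled partial record has no week to fill, so the error vanishes.

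**Simulation with the SAP's 7/days rule.** 200 per arm, no true difference, random dropout, skewed daily use capped at 3,000 mg, 0% or 30% never-users, week-specific arm mean as the fill, two-group test, 8,000 trials per cell (Monte Carlo SE about 0.25 points).

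| When leavers go | Alpha, 17% loss | SE ratio, 17% loss | Alpha, 10% loss |
|---|---|---|---|
| Week 4 | 5.0–5.4% | not tabulated | 5.0–5.1% |
| Days 15–27 | 5.6–5.7% | 0.97–0.98 | 5.1–5.5% |
| Evenly, Days 1–27 | 6.8–6.9% | 0.92–0.93 | 5.8–6.1% |
| Week 1 | 8.8–9.4% | 0.85–0.87 | 6.7–7.4% |
| No diary data (extreme) | 9.8–10.3% | not tabulated | 7.9–8.0% |

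At 5% loss all cells lie between 4.8% and 6.4%. The completers-only ANOVA stays at 4.5–5.4% throughout. A second simulation with eight assumed pooled sites and the catastrophizing group in the model gave, at 17% loss, 4.4–4.7% (Week 4), 6.8–7.2% (even) and 8.7–8.8% (Week 1), so leaving out those factors does not drive the result.

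**Check of the remedy.** Predictive mean matching within arm, 20 imputations, Rubin's rules, 30% never-users, 2,000 trials (Monte Carlo SE about 0.5 points). The informative-dropout rows rest on assumed rates of 12% against 22% by arm, with above-median users leaving three times as often.

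| Dropout | Mean fill | Completers | MI |
|---|---|---|---|
| Random 17%, Days 15–27 | 6.3% | 5.8% | 5.9% |
| Random 17%, even | 7.4% | 5.7% | 5.9% |
| Random 17%, Day 3 | 9.7% | 5.7% | 5.2% |
| Informative, even | 6.8% | 6.9% | 5.0% |
| Informative, end of Week 1 | 12.5% | 8.5% | 6.0% |
| Informative, Day 3 | 12.6% | 8.5% | 6.3% |

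In the informative rows the mean bias was 903–967 mg for completers and 16–121 mg for MI. A separate check (1,000 runs, 17% random loss, regression-based MI in the full ANOVA) gave MI 4.5% and fill 6.5% for even leaving, and MI 5.3% and fill 9.3% for Week 1.

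**The case against.** The strongest reply accepts the mechanism and disputes its size.

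- **17% is high.** The gap between 400 and 332 may include subjects outside the mITT set, which requires correct needle placement (SAP 7.2.3). The fill applies only to withdrawals, so a missed Week 4 visit by someone still keeping the diary triggers none. This stands, which is why 17% is an upper case.
- **9% needs everyone to leave in Week 1.** Protocol 3.5.5 says that after an early termination before Week 4 "the subject should be encouraged to continue in the study until W4 (D29), if possible". This stands too. With 10% loss spread evenly, the excess is about one point.
- **The endpoint is late and has company.** A completers-only ANOVA is planned, and SAP 7.12.6.14 to 7.12.6.16 analyse time to first rescue dose, proportion using rescue and rescue-free days without a mean fill. Those are different endpoints and do not correct this interval. The completers analysis is a real safeguard under random dropout, but it drifts when heavier users leave more often.
- **The remedy is not decisive everywhere.** For leaving on Days 15–27, MI (5.9%) is no better than completers (5.8%) and only slightly below the fill (6.3%), within simulation error. It also keeps the 7/days scaling, itself a single imputation. The NPRS precedent in SAP 7.12.3 is a placebo-based sensitivity analysis, so only the pooling step carries over. All true. The gain is largest with early leaving.
- **Wording.** The SAP does not say whether the fill is that week's mean or the mean over all weeks. The figures here use the week-specific mean. Either reading inserts a constant.

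**Conclusion.** The concern holds. As written, the Week 4 analysis of cumulative rescue use reports a standard error that is too small whenever a full week is filled. At the assumed 17% loss the nominal 5% test runs at about 5% to 9%, and the reported standard error is about 0.85 to 0.98 of the true one for leaving before Week 4, depending on timing. At 10% loss the test runs at about 5% to 7%. About 10% is reached only if leavers have no diary record at all.

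These figures assume random dropout and withdrawal rates and timings that the documents do not give. No figure is claimed for the Week 12 analysis. The primary and key secondary conclusions are unaffected. The point is worth correcting because a biased interval will be reported in any case and the correction is cheap.

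**What to change.** In SAP 7.12.6.13, replace the arm-mean fill with multiple imputation of weekly milligrams within randomised arm, for example predictive mean matching on the subject's own observed weeks. Keep the scaling of the withdrawal week, fit the planned ANOVA to each completed data set, and combine by Rubin's rules with PROC MIANALYZE, the pooling step already planned for NPRS in SAP 7.12.3. Name this the lead analysis for the endpoint and the completers-only ANOVA supportive.

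The cost is a paragraph of SAP text and one more imputation model to program. At 17% loss the intervals become about 2–10% wider than with the mean fill, but about 8–9% narrower than completers-only. With even leaving, the mean standard errors were 1,576 mg (fill), 1,661 mg (MI) and 1,815 mg (completers): 1,661/1,576 = 1.05 and 1,661/1,815 = 0.92. Multiple imputation would not correct dropout driven by rescue use that was never recorded, and the SAP should say so.
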